### 5.2.2 Reference Therapy

Patients randomized to the BSC arm will receive standard of care therapy according to institutional guidelines and patient need. Best supportive care is intended to serve as study control for comparison with those patients randomized to receive defibrotide prophylaxis. Administration of BSC will begin on the first day of conditioning and continue until Day +30 post-HSCT or hospital discharge, whichever is sooner, or diagnosis of VOD, if applicable (see [Section 5.7.5](#) and [Section 5.7.6](#)).

### 5.3 Selection and Timing of Defibrotide Dosing for Each Patient

All patients randomly assigned to receive defibrotide prophylaxis and all patients who receive defibrotide subsequent to diagnosis of VOD will receive the same dosage (25 mg/kg/day divided into 4 equal doses of 6.25 mg/kg/dose) and will follow the same regimen (2-hour infusions every 6 hours). Each dose (infused over a 2 hour  $\pm$ 15 min infusion period) may be administered within  $\pm$ 1 hour of the scheduled dosing time provided that there is at least a 2-hour window between the end of an infusion and the start of the next infusion. Each of the 4 divided doses per day will be rounded to the nearest 10 mg for adults ( $>35$  kg) and the nearest 5 mg for children ( $\leq 35$  kg) to facilitate efficient drug administration.

### 5.4 Method of Assigning Patients to Treatment Arms

Patients will be randomly assigned to receive defibrotide prophylaxis or BSC in a 1:1 ratio in an open-label fashion after they qualify for participation in the study. The investigator or designee will access IWRS to obtain treatment assignments for patients eligible to participate in the study.

### 5.5 Randomization

A copy of the master randomization code will be provided to the head of the Sponsor's Quality Department or a designee in a sealed envelope, and the Sponsor will be blinded to the master randomization code.

Randomization will be stratified according to risk of developing VOD (high risk or very high risk, as defined in [Section 4.1](#)), age ( $>16$  years or  $\leq 16$  years), and country. If a patient meets both the high-risk and the very high-risk criteria, the patient will be classified as very high risk.

### 5.6 Blinding

This is an open-label study. To minimize potential for bias, the following blinding measures will be employed:

- The central reviewer of imaging studies will be blinded to study treatment assignment and all non-radiologic patient data (see [Section 6.3.1.2](#)).
- Members of the EPAC will be blinded to study treatment assignment, will not be employees of the Sponsor, and will not be otherwise involved in the study ([Section 6.3.1.3](#) and [Section 11.9.2](#)).

Defibrotide (JZP-381)  
Clinical Trial Protocol: 15-007 Version 4.0

Jazz Pharmaceuticals, Inc.  
20 August 2018

---

Details of Sponsor blinding will be provided in a separate document.

## 5.7 Prior and Concomitant Therapy

### 5.7.1 Prior Medications

All medications and therapies taken from the time of screening through baseline will be recorded as prior medications. All previous anticancer treatments will also be recorded.

### 5.7.2 Medications for Conditioning Prior to HSCT

All medications and therapies (including radiation therapy) planned to be administered as part of the conditioning regimen (also known as the preparative regimen) will be recorded. In addition, actual doses and administration will be recorded. Patients who do not proceed to myeloablative conditioning (inclusion criterion #2(i) in [Section 4.1](#)) will be identified.

### 5.7.3 Concomitant Medications

All medications and therapies taken between baseline and Day +60 post-HSCT will be recorded as concomitant medications. Medications and therapies administered as BSC (for both DP and BSC arms) will also be recorded.

### 5.7.4 Graft-versus-Host-Disease Medications

Graft-versus-host disease prophylaxis should be administered according to institutional guidelines.

For patients who develop VOD per modified Seattle criteria as assessed by the investigator, use of sirolimus (also known as rapamycin [Rapamune®]) must be discontinued, and substituted with alternate GvHD prophylaxis.

GvHD medications will be recorded as follows:

- Medications used for the prevention of GvHD: prophylaxis
- Medications used after the initial clinical or pathological diagnosis of GvHD: treatment

### 5.7.5 Permitted Medications

Best supportive care includes all medications per institutional guidelines and patient need. For medications prohibited for use in the study, see [Section 5.7.6](#).

### 5.7.6 Prohibited Medications

Medications that increase the risk of bleeding are prohibited within 24 hours of the first dose of study treatment (defibrotide prophylaxis or as rescue treatment for VOD) and throughout the duration of defibrotide administration. Medications that increase risk of bleeding may be administered in the BSC alone arm as per institutional guidelines and patient need but not

Defibrotide (JZP-381)  
Clinical Trial Protocol: 15-007 Version 4.0

Jazz Pharmaceuticals, Inc.  
20 August 2018

---

concomitantly with defibrotide while they are taking rescue treatment for VOD. These include, but are not limited to, systemic heparin, low molecular weight heparin, heparin analogs, alteplase (t-PA), streptokinase, urokinase, ATIII, and oral anticoagulants, including warfarin, and other agents that increase the risk of bleeding. Note: Patients may receive heparin or other anticoagulants for routine central venous line management, and intermittent dialysis or ultrafiltration. Fibrinolytic instillation for central venous line occlusion is also permitted. Heparin use is allowed throughout the study for patients in both treatment arms (up to a maximum of 100 U/kg/day).

Patients receiving BSC (i.e., randomized to the BSC arm and not being treated for VOD) should not receive defibrotide as part of their BSC regimen.

All investigational therapies are prohibited from use in this study, with the exception of defibrotide for treatment of VOD.

The Sponsor must be notified of any instances in which excluded therapies are administered.

## **5.8 Treatment Compliance**

Defibrotide will be administered by study site personnel, and all administrations will be recorded in the eCRF. Treatment compliance will be monitored throughout the study.

## **5.9 Packaging and Labeling**

Defibrotide will be supplied to the study sites by the Sponsor in vials containing 200 mg defibrotide at a concentration of 80 mg/mL.

All packaging and labeling operations will be performed according to current Good Manufacturing Practices (cGMP), GCP, and local requirements.

## **5.10 Storage and Accountability**

Defibrotide will be stored, inventoried, reconciled, and retained or destroyed according to applicable state and federal regulations and instructions from the Sponsor.

Unopened vials of defibrotide are to be stored according to the carton/vial label. Use the diluted defibrotide solution within 4 hours if stored at room temperature or within 24 hours if stored under refrigeration (2°C to 8°C). Partially used vials should be discarded.

The investigator or pharmacist will maintain accurate records of receipt of all defibrotide, including dates of receipt. Defibrotide must be kept in a secure area. Unused (or partially used) supplies must be accounted for on the drug inventory record. The receipt and dispensing of all defibrotide must be documented throughout the study and reconciled at study completion.

After the study has been completed and all drug accountability records have been completed and reviewed, all unused clinical supplies are to be disposed off per instructions from the Sponsor. The investigator must provide a written explanation for any missing study

Defibrotide (JZP-381)  
Clinical Trial Protocol: 15-007 Version 4.0

Jazz Pharmaceuticals, Inc.  
20 August 2018

---

treatment. One copy of the drug inventory record will be retained at the study site and the other will be retained by the Sponsor.

## **6 STUDY PROCEDURES**

### **6.1 Informed Consent/Assent**

All patients will provide their written informed consent or assent, as applicable, before any study-related procedures are performed. Parents/legal guardians or representatives of minor patients will also provide written informed consent in accordance with local Institutional Review Board (IRB)/Independent Ethics Committee (IEC) requirements.

Each patient's chart will have his or her signed informed consent form (ICF) and/or assent form for study participation attached to it. When the study treatment is completed and the eCRF has been monitored, the ICF will be kept in the investigator's central study file. Regulatory authorities may check the existence of the signed ICF in this central study folder. All patients will be given a copy of their signed ICF.

### **6.2 Medical History, Information Pertaining to Underlying Disease / Any Prior HSCTs, and Current HSCT**

#### **6.2.1 Medical History**

A complete medical history including standard body systems and any ongoing infections will be collected.

#### **6.2.2 Information Pertaining to Underlying Disease**

Information pertaining to the underlying disease, including date of initial diagnosis, date of recurrent disease, if applicable, prior treatment for diagnosis (e.g., surgery, radiation, chemotherapy), if applicable, will be collected. Information pertaining to any prior HSCTs, including type of graft, source of graft, degree of human leukocyte antigen (HLA) matching, and number of prior HSCTs, if any, will be collected.

Information will also be collected regarding previous history of liver disease (results of liver biopsies, previous hepatitis serology testing).

#### **6.2.3 Information Pertaining to Current HSCT**

Information pertaining to the current HSCT, including type of graft, source of graft, degree of HLA matching, number of prior HSCTs, if any, will be collected.

### **6.3 Efficacy Assessments**

Efficacy will be assessed through monitoring of hepatic function and signs and symptoms for development of VOD, VOD-associated MOD, resolution of VOD, and survival.

Defibrotide (JZP-381)  
Clinical Trial Protocol: 15-007 Version 4.0

Jazz Pharmaceuticals, Inc.  
20 August 2018

### 6.3.1 Primary Efficacy Assessment for Veno-Occlusive Disease-Free Survival by Day +30 Post-Hematopoietic Stem Cell Transplant

#### 6.3.1.1 Development of Veno-Occlusive Disease

Diagnosis of VOD per the modified Seattle criteria requires at least 2 of the following criteria:

- Total bilirubin >2 mg/dL or 34  $\mu$ mol
- Hepatomegaly post-HSCT (with or without right upper quadrant pain) or an increase from baseline in hepatomegaly. Hepatomegaly (both adults and pediatrics) is defined as a >15% increase in liver size and an absolute increase of at least 1 cm in length in the mid-clavicular line compared with baseline as determined by ultrasonography
- Unexplained weight gain of  $\geq$ 5% above baseline or ascites

Note: Ascites “Yes” on EPAC or clinical diagnosis of VOD per the modified Seattle criteria is defined as the presence of any amount of free fluid greater than trace fluid in the abdomen as determined by ultrasonography in a patient with “ascites absent” at baseline (see Table 4 for details and definitions).

**Table 4 Ascites Assessment**

Ascites Assessment by Ultrasound		Ascites Assessment for EPAC or Clinical Diagnosis of VOD a
Ascites at Baseline	Ascites Post-baseline	
Absent b	Absent	No
Absent	Present	Yes
Present c	Absent	Not Evaluable d
Present	Present	Not Evaluable
Not Evaluable e	Absent or Present or Not Evaluable	Not Evaluable
Absent or Present	Not Evaluable	Not Evaluable

a For diagnosis of VOD using the modified Seattle criteria.

b Ascites “absent” at baseline or any post-baseline ultrasound examination is defined as trace ascites or no ascites as determined by ultrasonography on the specified ultrasound examination.

c Ascites “present” at baseline or any post-baseline ultrasound examination is defined as the presence of any amount of free fluid greater than trace as determined by ultrasonography on the specified examination.

d Ascites “Not evaluable” in the context of ascites assessment for EPAC or clinical diagnosis VOD per modified Seattle criteria means that ascites cannot be used when determining whether or not VOD is present.

e Ascites “Not evaluable” at baseline or any post-baseline ultrasound examination means the measurement was not obtainable for any reason on the specified ultrasound examination

EPAC= Endpoint Adjudication Committee; VOD=veno-occlusive disease.

Note: Liver size and ascites must be confirmed by ultrasound as physical examination is insufficient to document these parameters. All imaging should be made available to the central imaging facility.

Defibrotide (JZP-381)  
Clinical Trial Protocol: 15-007 Version 4.0

Jazz Pharmaceuticals, Inc.  
20 August 2018

Note: Baseline values for weight and bilirubin level will be obtained within 24 hours before the first dose of conditioning regimen for the patients in the DP arm and on the day that conditioning begins for patients in the BSC arm. Baseline values for hepatic size and presence of ascites will be obtained during ultrasound examination at the screening visit.

Histopathological evidence of VOD by liver biopsy is sufficient to confirm diagnosis of VOD with or without clinical characteristics of the disease; liver biopsy is not mandatory and should only be obtained if this can be safely performed. A standardized protocol for the histopathological analysis of liver biopsy specimens is provided in [Appendix 3](#). When liver biopsy is indicated, it is recommended that the wedged hepatic vein pressure gradient (WHVPG) also be measured, if this can be safely performed.

Total bilirubin values will be measured and physical examinations will be performed during screening. An abdominal ultrasound to assess liver and ascites will be performed to evaluate the status of VOD according to a standardized protocol provided by the central imaging laboratory (see [Appendix 4](#)). If assessment of Doppler flow pattern is otherwise performed, these results will be captured in the eCRF. Ultrasounds may be performed more frequently than at the time points specified in [Appendix 1](#) and [Appendix 2](#), as clinically indicated. Clinical signs or symptoms that may require more frequent ultrasound assessments for VOD diagnosis include the following:

- Evidence by physical examination of hepatomegaly (or worsening from baseline) or ascites (with or without right upper quadrant pain)
- Unexplained weight gain of  $\geq 5\%$  from the baseline value
- Total bilirubin  $>2$  mg/dL or  $34$   $\mu\text{mol}$

### 6.3.1.2 Central Review of Imaging Studies

All imaging studies will be reviewed at a central imaging facility by personnel who will be blinded to study treatment and all non-radiologic data.

The central imaging facility will address the following:

- Liver size (change from baseline, hepatic length in the mid-clavicular line, associated date)
- Ascites (“absent/present/not evaluable”, description, associated date);  
“Ascites present” at baseline or any post-baseline ultrasound examination is defined as the presence of any amount of free fluid greater than trace as determined by ultrasonography on the specified examination. If there is trace ascites or no ascites on a specific ultrasound examination, this is considered “ascites absent.” If the presence of ascites is not obtainable for any reason during an ultrasound examination, then the ultrasound finding for ascites will be considered “not evaluable” (see [Table 4](#) for details).

Defibrotide (JZP-381)  
Clinical Trial Protocol: 15-007 Version 4.0

Jazz Pharmaceuticals, Inc.  
20 August 2018

---

### 6.3.1.3 Endpoint Adjudication Committee

Development of VOD for individual patients will be adjudicated by members of the EPAC, who will be blinded to study treatment. The EPAC will receive weight data, clinical laboratory test results, imaging reports from the central imaging facility, biopsy data (any organ, when available), and additional data as clinically indicated. The EPAC will base its adjudication decision on review of the following as outlined in the central imaging charter:

- Weight gain  $\geq 5\%$  from baseline (yes/no, date of assessment)
- Total bilirubin  $> 2$  mg/dL (yes/no, date of assessment)
- Imaging reports from the central imaging facility providing data regarding liver size and/or ascites
- Physical exam data (assessment of right upper quadrant pain)
- Additional data as clinically indicated
- Biopsy data (any organ)
- For hyperbilirubinemia/liver dysfunction (such as GvHD, intravascular hemolysis, viral infection(s), prior liver disease)
- For ascites and/or weight gain (fluid overload, cardiac failure, capillary leak syndrome)

### 6.3.2 Key Secondary Efficacy Assessment

Assessment of the key secondary efficacy variable consists of monitoring VOD-free survival by Day +100 post-HSCT. Diagnosis of VOD will be made as described for the primary efficacy assessment (see [Section 6.3.1](#)).

### 6.3.3 Other Secondary Efficacy Assessments

Other secondary efficacy assessments include monitoring for incidence of VOD by Day +30, Day +100, and Day +180 post-HSCT, VOD-free survival by Day +180 post-HSCT, relapse of disease, VOD-associated MOD, and resolution of VOD.

#### 6.3.3.1 Venous Occlusive Disease-Free Survival by Day +180 Post-Hematopoietic Stem Cell Transplant

For monitoring of VOD-free survival through Day +180 post-HSCT, the diagnosis of VOD by Day +100 post-HSCT will be made by EPAC as described for the primary efficacy assessment (see [Section 6.3.1](#)), and the diagnosis of VOD after Day +100 post-HSCT will be based on investigator assessment.

#### 6.3.3.2 Relapse of Malignant Disease

Monitoring for relapse of malignant disease will vary as clinically indicated, and will be diagnosed according to institutional standards. Relapse of disease, if applicable, will be documented and recorded on the eCRF.

Defibrotide (JZP-381)  
Clinical Trial Protocol: 15-007 Version 4.0

Jazz Pharmaceuticals, Inc.  
20 August 2018

### 6.3.3.3 **Veno-Occlusive Disease-Associated Multi-Organ Dysfunction**

Veno-occlusive disease-associated MOD is defined as renal or pulmonary dysfunction in the presence of VOD. Renal dysfunction will be diagnosed if any of the following criteria are met by Day +30, Day +100, or Day +180 post-HSCT:

- Serum creatinine  $\geq 3$  times the value at baseline or the lowest value during HSCT conditioning
- Creatinine clearance (CrCl)  $\leq 40\%$  of the value at baseline or the greatest value during HSCT conditioning, calculated using Cockcroft-Gault for adults and Schwartz formula for pediatric patients, or the glomerular filtration rate (GFR) (calculated if cystatin C is measured),  $\leq 40\%$  of the value at baseline or the greatest value during HSCT conditioning, ([Grubb et al. 2005](#); [Larsson et al. 2004](#)).
- Dialysis dependence  
Note: Renal dysfunction must be attributable to fluid overload or mechanical impingement from abdominal distention or hepatic enlargement and not due to nephrotoxic drugs (e.g., cyclosporine, amphotericin B).

Pulmonary dysfunction will be diagnosed if the patient requires oxygen supplementation using any of the following by Day +30, Day +100, or Day +180 post-HSCT:

- Face mask for at least 24 hours
- Bilevel positive airway pressure (BiPAP) device or
- Ventilator support  
Note: Oxygen supplementation by nasal cannula is not a criterion for pulmonary dysfunction. Pulmonary dysfunction must be attributable to fluid overload or mechanical impingement from abdominal distention or hepatic enlargement and not due to infection (e.g., pneumonia).

### 6.3.3.4 **Resolution of Investigator-Diagnosed Veno-Occlusive Disease and Veno-Occlusive Disease-Associated Multi-Organ Dysfunction**

Investigators will determine whether patients have resolution of VOD which requires that patients who develop VOD (according to investigator diagnosis) have not only resolution of their VOD, but also resolution of any VOD-associated MOD, if applicable and as defined below by Day +30, Day +100, or Day +180 post-HSCT:

- Resolution of VOD will be defined as follows:
  - For patients who had a total bilirubin value  $>2$  mg/dL attributed to VOD at any point while participating in the study, these patients must have:
    1. Total bilirubin  $<2.0$  mg/dL for 3 consecutive days, and
    2. Resolution of VOD-associated MOD, if applicable

Note: Resolution of abnormal total bilirubin level as a parameter for resolution will be omitted if there is documented alternate cause for additional hepatic injury (e.g., GvHD of the liver).

Defibrotide (JZP-381)  
Clinical Trial Protocol: 15-007 Version 4.0

Jazz Pharmaceuticals, Inc.  
20 August 2018

- For patients who never had a total bilirubin value >2 mg/dL, or total bilirubin was >2 mg/dL and not attributed to VOD, these patients must have:
  1. Resolution of ascites or return of weight to baseline (for patients >20 kg at randomization) or weight adjusted for growth (for patients <20 kg), and
  2. Clinically significant decrease (return to baseline measurement) of liver size confirmed by ultrasound, and
  3. Resolution of VOD-associated MOD, if applicable, and
  4. Normalization of the portal flow (if present at VOD diagnosis) and documented by ultrasound
- Resolution of VOD-associated MOD will be defined as follows:
  - Renal MOD
    1. Serum creatinine level <1.5 times baseline or the lowest value during HSCT conditioning, or CrCl (or optional GFR calculated if cystatin C is measured) >80% at baseline or the greatest value during HSCT conditioning, and
    2. No need for dialysis (intermittent or continuous veno-venous hemofiltration [CVVH])
  - Pulmonary MOD
    1. No need for supplemental oxygen by either face mask or BiPAP device for 3 consecutive days, and
    2. No need for ventilator support

The dates when resolution of VOD and resolution of VOD-associated MOD are met will be recorded.

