10.2.2.4 Incidence of VOD-associated MOD by Days +30 and +100 post-HSCT

VOD-associated MOD is defined for subjects as occurring if the investigator answers “Yes” to the question “Has the subject been diagnosed with VOD associated MOD?” in the eCRF. The number and proportion of subjects who develop VOD-associated MOD by Days +30 and +100 post-HSCT will be summarized and compared between the 2 treatment arms using a chi-square test.

The following summary will be provided:

- Summary of VOD-associated MOD

The following listing will be provided and will include the date of MOD and type of renal and pulmonary dysfunction:

- Listing of VOD-associated MOD

10.2.2.5 Resolution of VOD by Day +180 post-HSCT and Time to Resolution of VOD

Of those subjects who were diagnosed with VOD by Day +30 post-HSCT by the investigator, the proportion of subjects who have resolution of VOD by Day +180 post-HSCT will be summarized by treatment arm.

Time to resolution of VOD will be calculated as follows:

Time to resolution of VOD = [Date of VOD resolution] – [Date of VOD diagnosis by investigator]

If VOD does not resolve by Day +180 post-HSCT, the subject will be censored on the date of the Day +180 post-HSCT VOD resolution assessment. If the Day +180 post-HSCT VOD resolution assessment is missing, they will be censored on the date of the last VOD resolution assessment performed.

The following will be presented for VOD resolution by Day +180 post-HSCT:

- The number of subjects by treatment group who had an event and who were censored (either due to not having an event or for other reasons as described above).
- The p-value from a log rank test stratified by risk status and age group.
- The KM estimates of the NRM rate (%) with 95% CI.
- the KM estimate of median time to NRM in days (95% CI).
- The HR (95% CI) from a Cox proportional hazards regression model stratified by risk status and age group.
- A KM plot will be presented up to Day +180 post-HSCT for each treatment arm. The number of subjects at risk will be displayed at 10-day intervals.

The following summary will be provided:

- Analysis of VOD resolution by Day +180 post-HSCT

The following figure will be provided:

- Figure of VOD resolution by Day +180 post-HSCT

The following listing will be provided and will include whether or not VOD was resolved, the criteria met for resolution, and the date of resolution:

- Listing of VOD resolution

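### When bilirubin is waived for another liver injury and there was no MOD, the VOD resolution definition has no criterion left, so resolution status and date are undefined

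*Protocol*

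**What the plan says.** Protocol 6.3.3.4 defines resolution through two separate sets of criteria.

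- **First set.** This covers patients whose total bilirubin exceeded 2 mg/dL and was "attributed to VOD at any point while participating in the study, these patients must have" two things: bilirubin under 2.0 mg/dL for 3 consecutive days, and "Resolution of VOD-associated MOD, if applicable".
- **Note under the first set.** "Resolution of abnormal total bilirubin level as a parameter for resolution will be omitted if there is documented alternate cause" for further liver injury; GvHD of the liver is the example given.
- **Second set.** This covers patients whose bilirubin never exceeded 2 mg/dL, "or total bilirubin was >2 mg/dL and not attributed to VOD, these patients must have" resolved ascites or weight back to baseline, liver size back to baseline on ultrasound, MOD resolved if applicable, and normalized portal flow if that finding was present at diagnosis.

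The same section assigns the decision: "Investigators will determine whether patients have resolution of VOD", by the definitions that follow.

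Protocol 9.8.3.5 dates resolution at the day the last criterion was met. SAP 10.2.2.5 says that "the proportion of subjects who have resolution of VOD by Day +180 post-HSCT will be summarized by treatment arm". It computes time to resolution as the resolution date minus the investigator's diagnosis date, with a stratified log-rank p-value and a hazard ratio. Its only censoring rules are for VOD that has not resolved.

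**The concern.** The note removes a criterion without saying what takes its place. For a patient without MOD, the bilirubin test was the only one that applied, so the waiver leaves the definition empty. The patients concerned have a second liver problem on top of VOD, and they are the ones for whom a clear endpoint rule is most needed.

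Two secondary endpoints depend on the result: the proportion resolved by Day +180 and the time to resolution. The study is open-label, and resolution is judged by the investigator rather than by the blinded adjudication committee, so unblinded discretion fills the gap. The trigger may also be related to treatment. Comparing acute GvHD between arms is itself a study objective, and Protocol 1.3 reports that in the earlier pediatric trial all-grade acute GvHD by Day +30 in allogeneic patients was 34% with defibrotide against 53% in controls. Those figures are not liver-specific. If a similar pattern held for the liver, the waiver would apply more often in the BSC arm and could credit that arm with resolutions that no measurement supports.

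**Working it through.** The plan states no figure here to reproduce. The check is mainly logical.

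**1. Who is in the first set.** Membership depends on attribution of bilirubin to VOD at any time in the study. A later GvHD diagnosis does not move the patient to the second set.

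**2. Apply the note.** Write the first-set rule as: resolved = B and M, where B is the bilirubin criterion and M is MOD resolution, required only if MOD occurred.

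- No waiver, no MOD: B remains.
- No waiver, MOD: B and M remain.
- Waiver, MOD: M remains, so status and date are defined.
- Waiver, no MOD: nothing remains.

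**3. Look for a fallback.** The note does not refer to the second set. The resolution assessments in Protocol 7.4.1.2, 7.4.2.1 and Appendix 2 list ascites and weight among the items reviewed, but no text makes them criteria for first-set patients. SAP 10.2.2.5 has no rule for the case.

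**4. Look for the date.** Protocol 9.8.3.5 needs a last criterion, and in the fourth case there is none. Possible readings are the day the other injury is documented, the next resolution assessment, a date the investigator chooses, or the VOD diagnosis date (time 0) if the other injury was documented first. These give different times in the log-rank test.

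**5. Overlap of trigger and criterion.** Protocol 6.8.5 monitors and stages liver GvHD by total bilirubin, starting at 2 to 3 mg/dL for stage 1. The measurement that can support the waiver is therefore the one being waived.

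**6. Size, by assumption only.** Share affected = f × p × m, where f is the fraction of VOD cases in the first set, p the fraction of those with a documented alternate liver injury, and m the fraction of those without MOD. None of these is in the documents. Assume p = 0.10 to 0.20 and m = 0.7.

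- f = 1: 0.10 × 0.7 = 7%, to 0.20 × 0.7 = 14%.
- f = 0.5: 3.5% to 7%.

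With an assumed 60 to 75 investigator-diagnosed cases and f = 1, that is 60 × 0.07 = 4.2 to 75 × 0.14 = 10.5 patients. With f = 0.5 it is 2.1 to 5.25. The design rates give 0.14 × 200 + 0.28 × 200 = 28 + 56 = 84 VOD-or-death events, and Protocol 9.3 expects an average of 68. Both include deaths, so 75 VOD cases is high unless investigators diagnose more often than the adjudication committee.

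**The case against.** A reader might infer that VOD counts as resolved on the day GvHD is recorded. The documents do not say so. No text sets that date, the investigator decides status, and the SAP uses a recorded date and lists the criteria met. A patient with persisting ascites and high bilirubin is resolved only if the investigator records it. This objection stands, and it limits the point to an undefined status and date. It does not remove the point, because investigators are told to apply the definition and here the definition is empty.

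A reader might also take 7 to 14 percentage points as the error in the resolution proportion. That would require every VOD case to be in the first set and no affected patient to resolve by Day +180 under any other rule. Neither is supported. A patient who would resolve by Day +180 anyway shifts only the timing.

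It is fair to add that ordinary first-set patients are never asked for ascites, weight, liver-size or portal-flow tests either. Their absence comes from the first set itself, not from the note. Using them for waived patients is stricter than the rule for their peers, which is a real cost of the fix.

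Finally, these are non-key secondary endpoints with nominal p-values, in a subgroup defined after randomization, and the proportion is only summarized. That bears on priority, not on whether the gap exists.

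**Conclusion.** The point holds in a limited form. For patients whose bilirubin above 2 mg/dL was attributed to VOD, who have a documented alternate liver injury and who had no MOD, the stated rule leaves no criterion. Status is met vacuously or by unblinded judgement, and the protocol's resolution date is undefined. Patients with MOD and patients in the second set are unaffected.

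The number affected cannot be found from the documents. The 3.5% to 14% range is an upper illustration under assumed inputs. A difference between arms is possible but conditional on liver GvHD differing by arm, for which the documents give no liver-specific figure. No primary or key secondary analysis depends on this. It is a cheap improvement to a secondary endpoint.

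**What to change.** Confine the change to the endpoint derivation in SAP 10.2.2.5, settled before database freeze:

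- Do not count a patient as resolved on the bilirubin omission alone.
- When bilirubin is omitted and no MOD occurred, derive analysis status and date from the measurements in the protocol's existing second set: ascites or weight, liver size on ultrasound, and portal flow where recorded. Use the date the last of these is met.
- If they are not met, censor at the last VOD resolution assessment.
- Flag these patients in the existing resolution listing.
- Add a sensitivity analysis censoring them at the date of omission.

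The cost is SAP wording and some programming; daily or twice-weekly weights and weekly ultrasounds are already scheduled in Protocol 7.4.1.2 and 7.4.2.1. The downside is that some patients will have later resolution dates or none. Data may also be missing: weekly ultrasounds after discharge run only until resolution, and Doppler results are captured only if the test was otherwise performed (Protocol 6.3.1.1).

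Separately, Protocol 5.2.1.2 continues rescue treatment until VOD resolution or discharge, so it relies on the same term. Sections 6.3.3.4 and 5.2.1.2 must be reconciled; no treatment rule is proposed here.
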